## Objective

To confirm the safety, feasibility and advantages by comparing the perioperative variables, postoperative functional and oncological outcomes of patients with ultralow rectal cancer treated by laparoscopic traditional distal rectal dissection vs. by transanterior obturator nerve gateway approach.

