### ➤ Exclusion criteria

- 1) The patient had previous abdominal surgery that will significantly infect the laparoscopic procedures;
- 2) Patients requiring emergency surgery owing to intestinal obstruction, perforation, or uncontrolled bleeding caused by tumor;
- 3) Patients with poor anal function preoperatively (Wexner score  $\geq 10$ );
- 4) ASA (American Society of Anesthesiologists) grading  $\geq IV$ ;
- 5) Pregnant patients;
- 6) Patients concomitant with severe mental illness;
- 7) The patient or the patient-authorized representative can't understand the contents and objectives of the study.

➤ **Withdraw criteria**

- 1) ISR cannot be performed by intraoperative evaluation and is replaced by Miles surgery;
- 2) Distant metastasis is confirmed intraoperatively or by postoperative pathological findings;
- 3) Patients had other primary tumors requiring surgical/drug treatment during the study, or had other illnesses that prevent the patient from continuing to participate this study;
- 4) Patients decide to withdraw from the study for any reason, or who are unable to complete the study because of any objective reasons.

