### **Treatment**

If the participant matches with the requirements for this study and agrees to take part in it, once hospitalized, the participant will complete the established preoperative tests including blood routine, the comprehensive metabolic panel, blood coagulation function, tumor markers, blood type, infectious disease screening tests, chest, abdominal and pelvic CT (Computed Tomography) scan and MRI, colonoscopy, echocardiogram, pulmonary function, venous duplex ultrasound of legs. All male patients will be routinely asked to fill

in the IIEF-5 sexual function scoring questionnaire preoperatively.

The following comprehensive treatment will be depended on the examination results:

➤ **Neoadjuvant therapy**

The treatment plan will be made in accordance with the NCCN (National Comprehensive Cancer Network) Guidelines for Diagnosis and Treatment of Colorectal Cancer (Version 1.2021).

Neoadjuvant chemoradiotherapy: Pelvis radiotherapy with a total dose of 50 Gy with 25 courses in 5 weeks. Neoadjuvant chemotherapy include single drug therapy: capecitabine (CAP, 1250 mg/m^2, BID) or double drug therapy: oxaliplatin combined with capecitabine (CapeOX, oxaliplatin 130 mg/m^2, day 1, capecitabine 1000mg/ m^2, day 1 ~ 14, then rest for 7 days, repeated every 3 weeks) or three-drug therapy (mFOLFOX6, oxaliplatin 85 mg/ m^2 intravenous infusion for 2 hours, leucovorin calcium 400 mg/m^2 intravenous infusion for 2 hours, 5-FU (fluorouracil) 400 mg/m^2 intravenous infusion for 1 day, Then 1200 mg/ m^2/d×2 days of continuous intravenous infusion with a total of 2400mg/m^2 for 46 ~ 48 hours, repeated every 2 weeks.

Abdominal and pelvic MRI and contrast enhanced CT will be routinely performed 6 to 8 weeks after neoadjuvant therapy to confirm the extent of tumor regression without new-found distant metastasis. Those whose clinical stage after neoadjuvant therapy changes from T4 to T3 will be seen as eligible in this study.

➤ **Surgical treatment**

● Preoperative preparation

- 1) Patients older than 60 years old or having a smoking history for over 10 years will receive lung ventilation training and atomization treatment for 3 days
- 2) Intestinal preparation will be done with oral cathartic medications 12-24 hours before surgery
- 3) Prophylactic antibiotics will be given once anesthesia is begun, the second antibiotics will be given if the operation lasts for over 3 hours

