- 4) Urethral catheterization will be routinely done preoperatively
- 5) If the patient refuses to accept the novel approach before surgery, they will be directly enrolled in the traditional group. If both approaches are acceptable to the patient, the decision whether to use the novel approach will be made according to the intraoperative

conditions (see operating procedures below).

- Operating procedures

General anesthesia; Modified lithotomy position (Fig. 1a); Establishment of pneumoperitoneum: Place a trocar 1cm above the umbilicus through which to establish pneumoperitoneum and keep the abdominal pressure as 12 mmHg (millimeters of mercury).

Trocar placement: above the umbilicus (trocar C, 10 mm), upper right and left quadrants (trocars B and D, 5 mm), lower right quadrant (trocar A, 12 mm), lower left quadrant (trocar E, 5 mm), the midpoint between the pubic symphysis and umbilicus (trocar F, 5 mm).

[figure not shown]

Fig.1 Patient position and trocar placement

Abdominal exploration: Explore the abdominal cavity in accordance with the principle of non-contact, from far to near step by step, explore the tumor finally.

The mesosigmoid and mesorectum are dissected from the right lateral rectum towards the root of the inferior mesenteric artery (IMA). The IMA is transected and ligated, so is the inferior mesenteric vein. Posterior space of the descending colon is dissected following opening the peritoneum beside the left rectum. The rectum in the pelvis is mobilized from posterior rectal space, anterior rectal space to bilateral rectal space successively. The lower edge of the tumor is marked by a clamp. The linear stapler is placed in the pelvis to clamp the distal rectum below the tumor to see if the transection can be done more than 1cm from the lower edge of the tumor. If yes, the distal rectum will be transected by the traditional approach (that means the patient will be assigned to the traditional group). The proximal bowel is transected through a small midline incision. Then the coloanal

anastomosis will be done intracorporeally. A surgical drain is placed in the pelvis and a terminal ileostomy is routinely performed. All incisions are closed.

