### **Statistics**

IBM SPSS (Statistical Package for the Social Sciences) Statistics 25 (IBM, Inc., Armonk, NY) will be used to perform statistical analyses. The *t* test and Mann-Whitney *U* test were used for quantitative data between groups. Qualitative data were compared by  $\chi^2$  or

Fisher's exact test and survival distributions were analyzed by log-rank test.

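### 1-year IIEF-5 in men would be compared between non-randomised groups without using the preoperative score already collected; IPSS, as a secondary matter, has no stated date and no baseline

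*Combined protocol and SAP*

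**What the plan says.** The Objective makes function part of the comparison: "To confirm the safety, feasibility and advantages by comparing the perioperative variables, postoperative functional and oncological outcomes of patients". The five listed primary outcomes are stapler angle, the change in that angle, distal margin, conversion and leakage. No functional score is among them.

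**IIEF-5.** Under Treatment, all men complete the questionnaire as part of the preoperative work-up ("in the IIEF-5 sexual function scoring questionnaire preoperatively"). Follow-up item 6 repeats the preoperative score and adds one at 1 year.

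**Group formation.** The study is non-randomised. Under Preoperative preparation, item 5: "If the patient refuses to accept the novel approach before surgery, they will be directly enrolled in the traditional group". Among patients who accept either approach, the group depends on whether the stapler can transect more than 1 cm below the tumour (Operating procedures).

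**Analysis.** Statistics is one short paragraph. It says that the t test and Mann-Whitney U "test were used for quantitative data between groups", and it names chi-square or Fisher's exact test and the log-rank test for other data. It names no covariate, change score, regression, stratification or propensity method.

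**IPSS.** It appears only under Postoperative management, item 2, with Table 1 asking about the past month. No day is given. It is absent from the preoperative work-up and from the Follow-up list. The flow chart has no readable content.

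**The concern.** Randomisation would balance preoperative sexual function on average. Refusal and stapler reach carry no such guarantee. If the men in the two groups start from different IIEF-5 scores, part of that difference carries into the 1-year scores and can pass for an effect of the approach, or hide one.

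The plan also leaves the contrast open. The between-group difference in the 1-year score minus the between-group difference in change equals the baseline difference, as an identity. Choosing between the two after seeing the data would therefore move the estimate by exactly the observed imbalance.

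For IPSS, one undated postoperative score with a one-month recall cannot separate new symptoms from old ones, nor lasting symptoms from passing ones. If it is completed in hospital, the recall month includes time before surgery.

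**Working it through.** **No plan figure to reproduce.** The protocol gives 100 experimental and at least 100 control patients without alpha, power, effect or SD. It gives no number of men, no IIEF-5 imbalance and no correlation. All inputs below are assumptions.

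**Inputs.** n = 60 men per group; within-group SD 1 at both times; baseline imbalance d = 0.3 SD; correlation rho = 0.3, 0.5, 0.7; two-sided 5% tests; no true effect of approach. The standard error of a difference in means is sqrt(2/60) = 0.1826 SD.

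No effect of approach can mean two things when groups differ at baseline.

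**Assumption A: no effect given baseline.** The expected 1-year difference is rho × d.
- Unadjusted 1-year test: ncp = rho × d / 0.1826 = 0.09/0.1826, 0.15/0.1826, 0.21/0.1826 = 0.49, 0.82, 1.15.
- Change score: shift −(1 − rho) × d = −0.21, −0.15, −0.09; SD sqrt(2(1 − rho)) = 1.183, 1.000, 0.775; absolute ncp 0.97, 0.82, 0.64.
- ANCOVA (regression on group and preoperative score): unbiased, because this assumption is the model it fits.

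**Assumption B: the baseline difference simply persists.** The expected 1-year difference is d.
- Unadjusted 1-year test: ncp = 0.3/0.1826 = 1.64 at every rho.
- Change score: shift 0.
- ANCOVA: bias (1 − rho) × d = 0.21, 0.15, 0.09, with standard error about sqrt(1 − rho²) × 0.1826; ncp about 1.21, 0.95, 0.69.

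Rejection rates (noncentral t; ANCOVA by simulation, 20,000 runs per cell):

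| Test | A: rho 0.3 / 0.5 / 0.7 | B: rho 0.3 / 0.5 / 0.7 |
|---|---|---|
| Unadjusted 1-year score | 7.8% / 12.9% / 20.7% | 37% / 37% / 37% |
| Unadjusted change | 16.1% / 12.9% / 9.7% | 5% / 5% / 5% |
| ANCOVA | about 5% throughout | about 22% / 15% / 10% |

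**Smaller imbalance.** Under A, with rho 0.5 and 60 men, the unadjusted 1-year test rejects 5.0%, 5.8% and 8.4% at d = 0, 0.1 and 0.2 SD.

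**No imbalance.** The gain is precision only. The ANCOVA standard error is sqrt(1 − rho²) = 0.954, 0.866, 0.714 of the unadjusted one. That is about 5%, 13% and 28% smaller, allowing for slightly less than the theoretical gain in samples of 60.

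**IPSS feasibility.** From 2020-12-01 to the protocol date 2021/9/7 is 280 days. Completion on 2025-12-01 with 3 years of follow-up puts the last operation near 2022-12-01, or 730 days after the start. With even accrual (assumed), 280/730 = 38% of patients had already been operated on and have no preoperative IPSS. Those operated on more than 90 days before the protocol date, (280 − 90)/730 = 190/730 = 26%, had also passed the 3-month point. None had passed 12 months.

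**The case against.** **Adjustment is not a cure.** The strongest objection is that ANCOVA holds its 5% level only if there is no effect given baseline. Groups form by refusal and anatomy, not by IIEF-5. A stable group difference, for example in age, could persist to 1 year; then the change score is correct and ANCOVA is not. This stands. A reader might infer that adjustment removes the bias. It does not do so in general, and the documents cannot say which assumption is nearer the truth. What survives is that adjustment improves on the unadjusted 1-year test under both.

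**The magnitude is assumed.** This also stands. Nothing in the protocol links stapler reach or refusal to erectile function, and with a small imbalance the inflation is slight.

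**Statistics does not name IIEF-5.** Correct. It would be too strong to say that the plan prescribes an unadjusted test of the 1-year score. The tests reach IIEF-5 only through the general rule, and the contrast is left unstated.

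**Baseline timing.** A reader might infer that the preoperative IIEF-5 is contaminated by radiotherapy. Treatment lists it among the admission tests and then says "The following comprehensive treatment will be depended on the examination results", with neoadjuvant therapy next. The more natural reading is a score taken before neoadjuvant therapy. The timing should be stated, but contamination is not shown.

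**Urinary harm is not ignored.** Day of catheter removal, residual urine, re-catheterisation and medication for dysuria are recorded. These cover early harm; they do not show lasting symptoms.

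**Conclusion.** The point holds as a gap in the analysis of a supporting functional outcome. With 60 men per group, 0.3 SD imbalance and rho 0.3 to 0.7, all assumed, adjustment lowers the rejection rate of the 1-year comparison from 8%–21% to about 5% under one null, and from 37% to about 22%–10% under the other. With no imbalance it still improves precision. It does not always beat the change score, which is why both should be reported.

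A reader might go further and infer that the trial's main conclusions are compromised by this gap. IIEF-5 and IPSS are outside the listed primary outcomes and IIEF-5 covers men only, so this point does not reach those conclusions.

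The IPSS gap is real in the readable text but secondary, since it is about data collection and cannot be fully repaired for patients already operated on. The change to Statistics is worth making because it costs no data.

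**What to change.** **In Statistics (main change).** State that 1-year IIEF-5 in men is compared by a regression on group with two covariates: the preoperative score and neoadjuvant radiotherapy (yes/no), which precedes the grouping. Use robust standard errors, as the score is bounded. Report the between-group difference in change as a sensitivity analysis. Show baseline scores and the number of men with both scores by group. State whether the preoperative score was taken before or after neoadjuvant therapy, and that other confounding from the way groups form remains. Cost: a few sentences; both IIEF-5 scores are already collected.

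**IPSS (secondary).** Add the questionnaire before surgery and at the existing 3- and 12-month contacts, keep the early urinary measures, and adjust later scores for baseline where there is one. Cost: one seven-item form at three contacts. The downside is the roughly 38% of patients without a baseline and, within them, the roughly 26% already past 3 months at the protocol date (even accrual assumed). For these patients only unadjusted later scores can be reported, with numbers per group. If the change is made at the protocol date, every surviving patient can still give a 12-month score.

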## **Methodology**

Prospective, Non-randomized, Interventional, Controlled

*The Biomedical Research Ethics Committee of Peking University First Hospital* is overseeing the research. ([contact]; Email: [[contact]](mailto:[contact]); Address: [name])

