### **Sample size**

Two groups are designed, patients who are to receive the traditional approach to transect the distal rectum are assigned to the control group, patients who are to receive the transanterior obturator nerve gateway approach to transect the distal rectum are assigned to the experimental group. 100 cases are to be enrolled for the experimental group and not less than 100 cases are to be enrolled for the controlled group.

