If the distal rectal transection cannot be done more than 1cm from the lower edge of the tumor, the anterior obturator nerve gateway approach will be used (that means the patient will be assigned to the experimental group). The steps are as follows: The peritoneum covering the ureter and external iliac artery is opened more than 2 cm across the vas deferens (male) or round ligament (female). The Retzius space and vesicohypogastric fascia are exposed. The obturator vessels and obturator nerve are properly identified. Care should be taken to avoid any injury when using energy devices near the obturator nerve. The gateway is then opened through the TME (total mesorectal excision) compartment and the lateral compartment. If necessary, an “endoloop” can be placed through the gateway, and the bundled S2-4 nerves, ureter and bladder vessels are gently retracted toward the cranial direction to widen the gap. The linear stapler is placed in the gateway to vertically transect the distal rectum. The following procedures are the same with the traditional group as described above.

During the operation, the following variables will be recorded: the angle between the linear stapler and the rectum, distance from the lower edge to the resecting margin, whether the operation converted to transanal approach, operative time, bleeding volume, anastomotic height from anal verge and the length of the stapling line.

➤ **Postoperative management:**

The following information will be recorded:

1) Vital signs (body temperature, pulse rate, respiration rate, blood pressure) are routinely monitored, gross volume of fluid input and output will be recorded every 24h, blood routine, the comprehensive metabolic panel and coagulation function tests will be performed every 3 days.

2) The time of catheter removal (days after operation), residual urine volume in the bladder will be measured by ultrasound examination. Whether there is a request to be re-catheterized or take oral medication to relieve the dysuria. All patients will be asked to fulfil the IPSS (International prostate symptom score) questionnaire to assess urinary function.

**Table 1.** International prostate symptom score assessing urinary function

In the past month:	Not at All	Less than 1 in 5	Less than Half the	About Half the	More than Half	Almost Always
--------------------	------------	------------------	--------------------	----------------	----------------	---------------

		Times	Time	Time	the Time	

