1. Incomplete Emptying How often have you had the sensation of not emptying your bladder?	0	1	2	3	4	5
2. Frequency How often have you had to urinate less than every two hours?	0	1	2	3	4	5
3. Intermittency How often have you found you stopped and started again several times when you urinated?	0	1	2	3	4	5
4. Urgency How often have you found it difficult to postpone urination?	0	1	2	3	4	5
5. Weak Stream How often have you had a weak urinary stream?	0	1	2	3	4	5
6. Straining How often have you had to strain to start urination?	0	1	2	3	4	5
	None	1 Time	2 Times	3 Times	4 Times	5 Times
7. Nocturia How many times did you typically get up at night to urinate?	0	1	2	3	4	5
Total Score						

Score: 1-7: Mild 8-19: Moderate 20-35: Severe

- 3) The time of pelvic drain removal (days after operation)
- 4) Whether complicated with anastomotic leakage, ileus and long-lasting (more than 5 days) pulmonary or abdominal infection
- 5) All information of the pathologic report.
- 6) Postoperative hospital stay (days)

➤ **Postoperative chemoradiotherapy**

Radiotherapy program is the same with the neoadjuvant therapy. Chemotherapy will be advised for patients with stage II cancer accompanied with the following high-risk factors: histologically poorly differentiated with normal mismatched repair or stable microsatellite (MSS), pT4 (pathological stage T 4), vascular/nerve invasion, preoperative intestinal obstruction or perforation, ≤ 12 lymph nodes retrieved and R1 resection. The chemotherapy program is the same with neoadjuvant chemotherapy. If mismatch repair defect (dMMR) or high-level microsatellite instability (MSI-H) is confirmed by pathology, chemotherapy

will not be advised. Patients with stage III cancer will routinely receive chemotherapy.

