7) 3-year tumor-free survival (month): The time from operation to confirmation of tumor's local recurrence or distant metastasis. The end point of the patient lost to follow-up is the date of loss. 30 days is defined as one month

8) 3-year overall survival (month): The time from operation to death. The end point of the patient lost to follow-up is the date of loss. 30 days is defined as one month

9) Stoma closure time (months since operation). Anal function is assessed by Wexner scale 3 months and 12 months after stoma closure, respectively.

**Table 3.** Wexner score assessing anal function

Type of Incontinence	Frequency				
	Never	Rarely	Sometimes	Usually	Always
Solid	0	1	2	3	4
Liquid	0	1	2	3	4
Gas	0	1	2	3	4
Wear Pad	0	1	2	3	4
Lifestyle altered	0	1	2	3	4

Never - 0

Rarely - Less than once a month

Sometimes - Less than once a week or once a month

Usually - Once a day or once a week

Always - Once a day or more

Score: 0 Perfect; 20 Complete Incontinence

(As to possible risks and benefits of participating in this trial, see details in the *informed consent document*.)

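### Three-year survival is compared between non-randomised groups by an unadjusted log-rank test, so any imbalance in stage or neoadjuvant therapy could bias the comparison in either direction

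*Combined protocol and SAP*

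**What the plan says.** - **Design.** Methodology describes the study as "Prospective, Non-randomized, Interventional, Controlled".
- **Assignment.** Two rules in the Treatment section set the group. The first is patient choice: "If the patient refuses to accept the novel approach before surgery, they will be directly enrolled in the traditional group". For patients who accept both approaches, the surgeon tests stapler reach during the operation, and the gateway approach is used "If the distal rectal transection cannot be done more than 1cm from the lower edge of the tumor".
- **Outcomes.** Follow-up items 7 and 8 define 3-year tumour-free survival (local recurrence or distant metastasis) and 3-year overall survival. The Objective includes a comparison of oncological outcomes. Neither survival outcome is in the Primary outcomes list, which covers stapler angle, change in angle, distal margin, conversion and leakage.
- **Case mix.** The Inclusion criteria exclude distant metastasis and limit clinical T stage and tumour size, but place no limit on nodal status. The postoperative chemoradiotherapy text foresees both stage II and stage III disease. Neoadjuvant therapy depends on the work-up, and down-staged tumours are admitted: "Those whose clinical stage after neoadjuvant therapy changes from T4 to T3 will be seen as eligible in this study".
- **Analysis.** The only survival method is in Statistics: "survival distributions were analyzed by log-rank test". No stratified test, regression model, matching, weighting or balance check appears anywhere in the document.
- **Data.** Postoperative management records "All information of the pathologic report".

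**The concern.** An unstratified log-rank test compares the two survival curves as they stand. It speaks to the surgical approach only if the groups have similar prognosis apart from the approach. Randomisation would give that in expectation. Here nothing does, and the plan has no analysis step in its place.

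Stage is a factor that the plan itself uses to decide on further treatment. If one group happens to hold more stage III or more pre-treated patients, the hazard ratio will move away from 1 with no effect of the approach. The opposite imbalance could hide a real difference. Both matter for a study whose Objective includes confirming safety. If the adjustment is not specified in advance, any adjustment added later will be open to the criticism that covariates were chosen after the results were seen.

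**Working it through.** **Inputs from the document.** Group sizes: "100 cases are to be enrolled for the experimental group and not less than 100 cases are to be enrolled for the controlled group" (taken below as 100 and 100). Horizon: 3 years. Test: log-rank, no strata.

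**Assumptions (not in the document).** Two-sided 5% level; share of stage III in each group; 3-year recurrence by stage; exponential event times censored at 36 months; no true effect of the approach.

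**Step 1. The plan's own figure.** The sample size comes with no alpha, power, effect or event count, so there is no survival calculation to reproduce. What 100 per group can support follows from the Schoenfeld formula with *d* events and equal groups: detectable HR at 80% power = exp[(1.960 + 0.842)/√(d/4)].
- 10% events: d = 200 × 0.10 = 20, HR = exp(2.802/2.236) = 3.50.
- 30% events: d = 200 × 0.30 = 60, HR = exp(2.802/3.873) = 2.06.

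Power for a true HR of 1.5 is about 15% with 20 events and 35% with 60.

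**Step 2. False hazard ratio from stage imbalance alone.** With a share *s* of stage III, 3-year recurrence is m = (1 − s) × 0.10 + s × 0.30, and HR = ln(1 − m₁)/ln(1 − m₀).

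| Stage III share | m₀ | m₁ | False HR |
|---|---|---|---|
| 35% vs 40% | 0.17 | 0.18 | 0.19845/0.18633 = 1.07 |
| 35% vs 50% | 0.17 | 0.20 | 0.22314/0.18633 = 1.20 |
| 30% vs 60% | 0.16 | 0.22 | 0.24846/0.17435 = 1.43 |
| 30% vs 60%, stage III recurrence 40% | 0.19 | 0.28 | 0.32850/0.21072 = 1.56 |

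Expected events in these rows are 100 × (m₀ + m₁) = 35, 37, 38 and 47.

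**Step 3. How often the plain test rejects.** Two sets of simulated trials (3,000 and 4,000 per scenario):
- 5 points: 5.1% (4,000-trial set).
- 15 points: 7.4% and 8.1%.
- 30 points: 20% and 19.2%.
- 30 points with 40% stage III recurrence: 33% and 32.5%.

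The Monte Carlo standard error near 8% is √(0.08 × 0.92/3000), about 0.5 points, so the two sets agree. In the three larger scenarios more than 90% of the false rejections went against the same group. A log-rank test stratified by stage rejected between 4.2% and 5.6% of the time.

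**Step 4. Other event rates.** With stage III shares of 30% vs 50% (20 points), again with no true effect:

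| 3-year event-free, lower / higher stage | Apparent HR | Plain | Stratified |
|---|---|---|---|
| 90% / 70% | 1.27 | 10.8% | 4.8% |
| 90% / 60% | 1.37 | 17.6% | 5.3% |
| 95% / 85% (about 18 events) | 1.27 | 7.4% | 4.7% |

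The last row shows what a rarer endpoint would do; overall survival may be closer to it. The hazard ratio is as biased as in the first row, but with fewer events the test rejects less often.

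**Step 5. What the stratified figures do and do not show.** Stratification returns the rate to about 5% because stage is the only confounder in these simulations. They do not represent selection by tumour height or pelvic anatomy.

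**The case against.** The strongest reply is that the imbalance is assumed. A reader might infer that the stapler test sends more advanced tumours to the gateway group, so that a false survival difference is built into the design. The documents do not support that. The Background attributes the difficulty to limited pelvic space, the test concerns reach below the lower edge of the tumour, and no passage links nodal stage to stapler reach. The eligibility limits, and withdrawal when metastasis is found, narrow the mix further. This stands: the point is conditional on imbalance.

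Three further objections also stand in part.
- With moderate imbalance most trials would show no significant difference: at 15 points about 92 to 93% would not reject. The bias in the estimate is present all the same.
- Survival is not a primary outcome, no margin or decision rule ties a safety conclusion to the log-rank p-value, and power is low. The comparison is therefore largely descriptive. That lowers the priority, but a descriptive hazard ratio should still not mix approach with case mix.
- Adjusting for stage and neoadjuvant therapy leaves the selection made by the stapler test. Among patients who accept both approaches that test fixes the group, so only those who refused the novel approach could supply controls who would have failed it.

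The other tests in Statistics are unadjusted too. That is a wider matter; this point is confined to survival.

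**Conclusion.** The point holds in conditional form. The plan compares 3-year tumour-free and overall survival between non-randomised groups with no account of stage or neoadjuvant therapy, so an imbalance in either could bias the apparent effect of the approach in either direction. Whether an imbalance will arise cannot be told from the documents.

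Under the main assumed rates the consequence runs from negligible at 5 points, through a modest distortion at 15 points, to roughly a fourfold false-positive rate at 30 points. These figures rest on assumed stage shares and recurrence rates, exponential times, equal groups of 100 and stage as the sole confounder.

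The primary outcomes are not touched by this point. The change should be made because it is cheap and gives a better comparison, not because the study fails without it. It would be wrong to conclude that the survival result will be false, or that adjustment would make the groups comparable.

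**What to change.** In Statistics, replace the survival clause with a prespecified comparison for both survival outcomes:
- a log-rank test stratified by pre-treatment clinical stage (stage III vs lower);
- a Cox model for approach, adjusted for pre-treatment clinical stage and neoadjuvant therapy (yes/no), reporting the hazard ratio and 95% interval;
- the same analysis with pathological stage as a sensitivity analysis, since neoadjuvant therapy can change it;
- the unadjusted curves, kept as description.

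Record pre-treatment clinical stage and receipt of neoadjuvant therapy explicitly on the case form. The eligibility and treatment text implies that both are known, but the lists of recorded variables name neither.

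Cost: wording, two case-form fields and minor analysis work, with no added patients or visits. Limits: with perhaps 30 to 50 events only two or three covariates can be supported, and stage and neoadjuvant therapy are likely to be correlated, which widens the interval. Selection by tumour height and pelvic anatomy is not removed, so the report should call the result an adjusted non-randomised comparison.
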